Despite laboratory data demonstrating the potential for RLX as an immune regulating molecule via PPARG²⁸ and GCR²⁹ pathways, and its safety in the limited settings in which it has been given to humans for treatment of systemic sclerosis³⁰ and ischemic heart disease ³¹, there have been no published preclinical or clinical studies addressing potential efficacy of RLX in inflammatory CNS disease, and only one presented abstract in which it was reported that patients diagnosed with MS had higher circulating levels of RLX, and reduced binding affinity to RXFP-1, when compared to normal controls, suggesting that the increase in circulating RLX was the result of loss of RLX-RXFP-1 regulatory feedback mechanisms. Further analysis revealed that there was structural abnormality in the MS patients' RLX due to a mutation in the B- chain binding cassette of RX ([name] and [name], personal communication).

RESEARCH STRATEGY

1. Because of the potential benefits of using a human molecule, with an encouraging safety profile, capable of regulating immune responses, we intend, in the future, to develop a therapeutic trial to assess the efficacy and safety of RLX in the treatment of patients with the relapsing form of MS. However there is no information available on such fundamental guestions as what serum and CSF levels of RLX are observed in patients with active versus stable relapsing MS, how these values compare to that found in human volunteers without MS or other inflammatory diseases, and whether RLX functions normally in subjects with active or stable MS. It is for this latter reason that we are proposing research to obtain baseline information on serum and CSF RLX levels in patients with MS, as well as to further study RXFP-1 receptor binding affinity for RLX in patients with active and clinically stable MS. Fortunately there are reliable, commercially available SIMOA assays to measure RLX serum and CSF concentrations and available cell-based RXFP-1 affinity assay systems.

PROTOCOL

Subjects:

All subjects will be age 18 to 60, non-pregnant females, since 65 to 80% of MS patients are female, and there are known gender differences in circulating RLX levels. Patients with known history of diabetes will also be excluded.

There will be 3 groups of subjects:

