Group 1 will consist of 10 subjects with suspected MS, who have had a clinical attack within the last 12 weeks, have at least one gadolinium-enhancing lesion on brain or spinal cord MRI taken within the prior 4 weeks, and for which they have not received any immunomodulating or immunosupressant medication. Because a subject in this group may have had a lumbar puncture in an emergency dept or in-patient setting for diagnostic purposes, prior to the investigators becoming aware of the patient, consent may be obtained post LP in this circumstance, and the analyses performed on residual CSF and serum, provided it had been handled in a manner not to interfere with the validity of the analyses. These subjects will also have had a urine pregnancy test performed prior to any relaxin analyses being performed on their samples.

Group 2 will consist of 10 subjects with clinically stable definite MS, with no evidence of clinical relapse for at least the past 12 weeks, and have no gadolinium enhancing lesions on MRI in the prior 12 weeks. These subjects will fulfill the Revised (2017) McDonald's Criteria for the Diagnosis of MS.

Group 3 will consist of 10 subjects without evidence of inflammatory systemic or inflammatory CNS disease, who require CSF removal for some other cause, such treatment of benign intracranial hypertension or as part of the procedure for insertion of an intrathecal medication delivery system.

Study Procedures:

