These analyses will provide us with quantitative data re: baseline RLXIevels in serum and CSF in subjects with and without known inflammatory CNS disease, as well as alterations in RLX receptor affinity that may occur, and determine whether there are differences in serum/CSF RLX levels and RLX receptor affinities during acute inflammatory and stable states in patients with the relapsing form of MS.

INSTITUTIONAL SUPPORT

The Providence Brain and Spine Institute's clinical research team consists of a manager, two full-time research nurses, five full-time clinical research coordinators (CRC), and 3 part-time clinical research assistants. In 2012, the team supported more than 30 active clinical trials in Alzheimer's disease, ALS, multiple sclerosis, Parkinson's disease, and stroke. The research staff has the experience and skills in conducting cooperative group trials, industry-sponsored trials, and investigatorinitiated studies. For each trial, the research staff works closely with the investigators to coordinate study activities, collect clinical research data, track patient and study status, and perform quality assurance activities regularly. The research team is familiar with clinical trials that require multiple specimen collections, diagnostic testing, and neurological and other clinical assessments. The MS Center has 4 full-time providers (5 MS neurologist and 1 NP) and a team of clinical support staff that take care of close to 3,000 MS patients. The group has successfully collaborated with industry and federally-funded sponsors, clinical research organizations, investigators, and ancillary services facilities on more than 30 MS studies in the past 5 years.

For the performance of the serum and CSF RLX and Sema4A levels and RXFP-1 RLX receptor affinity analyses, commercial and university laboratories will be employed as noted in the protocol.

REFERENCES

1. Weinshenker BG. Databases in MS research: pitfalls and promises. Mult Scler 1999;5:206-211.

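### Only the control group must be free of systemic inflammatory disease, so comorbidity in the MS groups can distort the MS-versus-control relaxin contrast

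*Combined protocol and SAP*

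**What the plan says.** The criteria common to all three groups stand at the start of the Subjects section: "All subjects will be age 18 to 60, non-pregnant females", and "Patients with known history of diabetes will also be excluded". Diabetes is the only comorbidity excluded for everyone.

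The group definitions follow:

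- Group 1: "Group 1 will consist of 10 subjects with suspected MS, who have had a clinical attack within the last 12 weeks", with an enhancing lesion on recent MRI and a medication restriction, "for which they have not received any immunomodulating or immunosupressant medication".
- Group 2: "Group 2 will consist of 10 subjects with clinically stable definite MS, with no evidence of clinical relapse for at least the past 12 weeks", with no recent enhancing lesion and the 2017 diagnostic criteria met.
- Group 3: "Group 3 will consist of 10 subjects without evidence of inflammatory systemic or inflammatory CNS disease", who need CSF removal for another reason.

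The Research Strategy section asks "how these values compare to that found in human volunteers without MS or other inflammatory diseases". The close of the Assays section says that the analyses will give "baseline RLXIevels in serum and CSF in subjects with and without known inflammatory CNS disease". The Analysis section plans descriptive statistics and t-tests or nonparametric tests between groups. It names no covariate, stratification or sensitivity analysis.

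**The concern.** Systemic inflammatory disease is ruled out on one side of the comparison only. The groups are meant to differ on inflammatory CNS disease, but eligibility also lets them differ on systemic inflammation. The background sections present relaxin as an immune regulator with anti-inflammatory actions, so on the protocol's own rationale a second inflammatory disease could plausibly be related to relaxin level or receptor response.

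At stake is how an MS-versus-control difference is read. The results are meant to inform a later therapeutic trial in relapsing MS. A part of the difference that belongs to comorbidity would be credited to MS, or a real MS difference would be partly hidden if the comorbidity acts in the other direction. With 10 subjects per group, one affected subject is a tenth of the group.

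**Working it through.** **Eligibility, side by side**

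| Criterion | Group 1 | Group 2 | Group 3 |
|---|---|---|---|
| Age, sex, not pregnant, no known diabetes | yes | yes | yes |
| No inflammatory CNS disease other than the MS under study | not stated | not stated | yes |
| No systemic inflammatory disease | not stated | not stated | yes |
| Medication restriction | yes | not stated | not stated |

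Nothing elsewhere closes the gap. Study Procedures describes no recording of comorbid inflammatory disease, and the Analysis section describes no adjustment for it.

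**Inputs for a sense of scale**

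- From the documents: 10 subjects per group and an unadjusted two-group test.
- Assumed, because the documents give no figure: two-sided alpha 0.05, a within-group SD of 1, a fraction q of MS subjects with systemic inflammatory disease, and a shift of s SD in relaxin in those subjects. Illustrative range: q = 5–15%, s = 1–2.

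The plan states no effect size, SD, alpha or power, so there is no figure of its own to reproduce.

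**Expected bias**

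Bias in the MS-minus-control mean = q × s, since q is zero in Group 3 by design.

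- Lowest: 0.05 × 1 = 0.05 SD.
- Highest: 0.15 × 2 = 0.30 SD.

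**Chance that at least one of the 20 MS subjects is affected**

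1 − (1 − q)^20:

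- q = 5%: 1 − 0.95^20 = 64%.
- q = 15%: 1 − 0.85^20 = 96%.

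This shows that the situation is likely to arise under the assumptions. It does not measure bias. One affected subject in a group of 10 moves that group's mean by s/10, that is 0.1–0.2 SD.

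**False-positive rate with no true MS effect**

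Unadjusted t-test, normal data, 100,000 simulated studies per row, rounded to the nearest percent:

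| q | s | Bias (SD) | 10 v 10 | 20 v 10 (MS groups pooled) |
|---|---|---|---|---|
| 0% | – | 0 | 5% | 5% |
| 5% | 1 | 0.05 | 5% | 5% |
| 5% | 2 | 0.10 | 5% | 5% |
| 15% | 1 | 0.15 | 6% | 6% |
| 15% | 2 | 0.30 | 8% | 7–8% |

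Outside that range, at 10 v 10, the rate is about 11% for q = 20%, s = 2 and about 18% for q = 30%, s = 2.

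**Comparison with what the study can see**

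With 10 v 10, a t-test at alpha 0.05 has 80% power for a difference of about 1.32 SD. The assumed bias is 0.05/1.32 = 4% to 0.30/1.32 = 23% of that.

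**The case against.** The strongest defence is that the control definition is deliberate. The Research Strategy asks how MS values compare with people who have neither MS nor other inflammatory disease, and Group 3 delivers that. This stands: nothing is wrong with the Group 3 criterion. The gap is the lack of a counterpart in Groups 1 and 2, or of any handling in the analysis. It is also fair that this is a small baseline study with mainly descriptive aims, for which unrestricted comorbidity in MS patients is defensible.

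The Group 1 medication restriction may keep out some treated inflammatory disease. But it restricts medication rather than disease, its wording appears tied to the attack or lesion, and Group 2 has nothing like it.

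Three stronger readings are tempting, and the documents do not support them.

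- A reader might infer that an MS-versus-control difference could not be credited to MS at all. The assumed bias is small beside the detectable difference. The false-positive rate clearly leaves the neighbourhood of 5% only when comorbidity is common (about 20% or more) and its effect large (about 2 SD or more).
- A reader might infer that the active-versus-stable contrast is biased too. Neither MS group carries the exclusion, so the asymmetry cannot bias Group 1 against Group 2. Chance imbalance between two groups of 10 applies to any unrestricted characteristic.
- A reader might infer that systemic inflammation is known to alter relaxin. The background describes relaxin acting on immune function. It does not say that systemic inflammatory disease changes relaxin concentration or receptor affinity. The one reported difference in level is in MS, and it is attributed to lost receptor feedback and a structural abnormality of the peptide.

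**Conclusion.** The point holds as a limited one. Eligibility is asymmetric on systemic inflammatory disease, no other part of the plan offsets this, and the MS-versus-control comparisons can be distorted as a result. The size and direction cannot be known from the documents. Under an assumed prevalence of 5–15% and an assumed shift of 1–2 SD, the bias is 0.05–0.30 SD and the false-positive rate about 5–8% instead of 5%. Both inputs are assumptions, as are the normal data and the alpha of 0.05. On that range the comorbidity would more probably distort a difference than produce one. The case for acting rests on how little the remedy costs, not on a large expected bias.

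**What to change.** Leave the Group 3 criterion as written. Add one sentence to the all-subject criteria at the start of the Subjects section, for example: *Subjects must have no evidence of systemic inflammatory disease (other than MS in Groups 1 and 2), as judged from the medical history.* Use a no-evidence standard throughout. A known-history standard in its place would loosen what is now asked of controls.

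With the criterion applied to all three groups, q is zero on both sides and this source of bias disappears. No sample-size or power figure in the plan changes.

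If recruitment does not allow the exclusion, record systemic inflammatory comorbidity at enrolment under the subject code, and report the MS-versus-control comparisons with and without affected subjects. It has to be recorded in advance. Under the Confidentiality section, results return by code only, and the one person who can link codes to identities stays blinded to the results and does not share identities, so tracing an outlying value to a comorbidity later would be difficult.

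The cost is one sentence of eligibility text and a check of the medical history, with no extra procedure or sample. A few MS candidates become ineligible. The documents do not allow that number to be estimated, and it may matter most in Group 1, whose criteria are already narrow.

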PPARG knockout mice are more susceptible to developing EAE¹⁵, and PPARG antagonists block the neuroprotective effects of the TZDs in EAE²⁰. In limited studies in MS patients, PPARG expression is reduced in peripheral immune cells and these cells have reduced responsiveness to PPARG agonists¹⁴.

Relaxin biology overview:

Relaxins (RLX) are members of the insulin-relaxin peptide family^{21, 22}, that do not bind to insulin receptors and have no effects on glucose metabolism ²³. RLXs have been shown to regulate uterine contraction and cervical growth and softening during pregnancy²⁴, are vasodilators and promoters of angiogenesis and may be protective in ischemic cardiovascular disease ²⁵. RLX may also affect immune function, promoting anti-inflammatory mechanisms. There are 3 known isoforms of RLX, RLX 2 being the most abundant circulating form in humans ²⁴. The gene responsible for RLX2 production is on chromosome 9²⁶, and is produced primarily in the corpus luteum of females, and heart, lung and kidney in males ²⁷. RLX acting via its receptor RXFP-1, increases cAMP production²² and nitric oxide production via NO synthetase²⁵.

Relaxin as an immune-modulating/regulating agent:

RLX increases PPARG transcription activity via the receptor Relaxin Family Petide-1 (RXFP-1)^{21, 23, 28}, without increasing PPARG mRNA or PPARG protein levels²⁸. RLX independently promotes PPARG via RXRP-1. In addition to its direct PPARG promoting effects, it also increases responsiveness PPARG to TZDs such as rosiglitazone²⁸. Given the known anti-inflammatory effects of PPARG promotion, this is one possible mechanism by which RLX impacts immune function. A second mechanism likely involves promotion of the glucocorticoid receptor (GCR) gene²⁹. Although found in cell nucleus, exogenous RLX can also

enter the cell nucleus and up-regulate GCR gene, leading to increased production of GCR protein, whereas corticosteroids down-regulate the production of GCR protein, thus creating a negative feedback that can be opposed by RLX competition for the GCR gene site. RLX blocks mitogen-induced production of IL-1, IL-6 and TNFa by macrophages via GCR gene activation, which can be blocked by the GCR inhibitor RU-486²⁹.

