Descriptive statistics will be applied to each variable show the distribution of the data. T-tests or nonparametric tests, depending on the type and distribution of the data, will be performed to compare the differences between groups.

Results:

Patients may be informed of the results of their study testing only after the completion and analysis of all study data.

CONFIDENTIALITY:

Each volunteer subject will be assigned a unique identification number, and this will be used to identify all samples sent to the diagnostic laboratory. The subjects' names, or any other personal identification information will never be available to the diagnostic laboratory or its members.

The results of the data will be returned to the primary investigators for analysis, identified by unique code only, and only after the data has been received will the group that each sample belongs to be identified. The sole individual who knows both personal identification and code numbers will always be blinded to the analytic results and will not share the identity of any subject with the other investigators.

ASSAYS

RLX 1 is measured in serum and CSF by DuoSet (R & D Systems # DY3257) sandwich ELISA. This method is RLX 1 specific and does not cross react with RLX 2, The range of sensitivity of the assay is from 100-10000 pg/mL., and is linear within this range.

RLX 2 is measured in serum and CSF by Quantikine (R & D Systems # DRL 200) sandwich ELISA. This method is RLX 2 specific and does not cross react with RLX 1. The range of sensitivity of the assay has been demonstrated to be 7.8 to 500 pg/mL and is linear within this range.

RLX-RXFP-1 affinity is measured as a function of cAMP production in human monocyte THP-1 cells expressing RXFP-1, following incubation with RLX 1 or RLX 2, both of which act as agonist ligands for this G protein-coupled receptor.

The cAMP levels will also be determined by a commercially available cAMP assay (Flash Plate RAI 125 cAMP assay-Perkin Elmer) in the presence and absence RX neutralizing antibodies. All RLX assays will be performed at Quanterix Labs, Lexington MA.

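### Three non-randomised, unmatched groups aged 18 to 60 are compared without adjustment; if relaxin varies with age and the groups differ in age, the two effects will be mixed

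*Combined protocol and SAP*

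**What the plan says.** The Subjects section sets the age range and sex: "All subjects will be age 18 to 60, non-pregnant females". Restriction to females is justified partly by known sex differences in circulating RLX. Age gets no comparable treatment.

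The groups are defined by clinical state:

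- "Group 1 will consist of 10 subjects with suspected MS, who have had a clinical attack within the last 12 weeks", with an enhancing lesion on recent MRI;
- "Group 2 will consist of 10 subjects with clinically stable definite MS", who volunteer for a lumbar puncture that their care does not require;
- "Group 3 will consist of 10 subjects without evidence of inflammatory systemic or inflammatory CNS disease", who need CSF removed for another reason, for example "as part of the procedure for insertion of an intrathecal medication delivery system".

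No matching or stratification is described. After descriptive statistics, the whole inferential plan is that "T-tests or nonparametric tests, depending on the type and distribution of the data, will be performed to compare the differences between groups". The combined document names no regression model, covariate or sensitivity analysis.

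Two statements bear on age indirectly. The Relaxin biology overview says that RLX 2, the most abundant circulating form, "is produced primarily in the corpus luteum of females". Study Procedures asks for a pregnancy test in patients with reproductive potential, which implies that some enrolled women will not have it.

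**The concern.** The groups reach the study by different routes: diagnostic work-up after an attack, volunteering while stable, and a procedure for an unrelated condition. Nothing in the design makes their ages alike, and the eligible span is 60 − 18 = 42 years. Corpus luteum activity depends on reproductive status, which changes over that span, so an age relation for RLX 2 is plausible on the plan's own account.

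Neither a t-test nor the usual rank test takes a covariate. If both conditions hold, the active-versus-stable and MS-versus-control contrasts will each contain an age component that the planned analysis cannot separate. The close of the Assays section says the study will determine whether RLX levels and receptor affinities differ between acute and stable disease. The Research Strategy presents this as groundwork for a therapeutic trial. The risk is that an age difference is read as a disease difference, or that it hides one.

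**Working it through.** The plan states no alpha, effect size, SD or power, so it has no figure of its own to reproduce. What follows is an illustration.

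**Inputs from the documents:** 10 per group; ages 18 to 60; unadjusted tests.

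**Assumed inputs:** two-sided 5% test; outcome (log RLX, say) with within-group SD 1; within-group correlation with age r = 0.2, 0.35 or 0.5; mean-age gap of 0.5, 1 or 1.5 within-group SDs of age; no true group effect.

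**Step 1, bias.** The unadjusted difference in means is off by r × gap. For r = 0.5 and a gap of 1 SD, that is 0.5 × 1 = 0.5 outcome SDs.

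**Step 2, false-positive rate.** The noncentrality is bias × √(n/2) = bias × √5 = bias × 2.236. In the same example, 0.5 × 2.236 = 1.118. A noncentral t on 18 df with critical value 2.101 then rejects 18.5% of the time. All settings:

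| Age gap | r = 0.2 | r = 0.35 | r = 0.5 |
|---|---|---|---|
| 0 | 5.0% | 5.0% | 5.0% |
| 0.5 SD | 5.5% | 6.6% | 8.3% |
| 1 SD | 7.1% | 11.5% | 18.5% |
| 1.5 SD | 9.7% | 19.9% | 35.5% |

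Simulation of the t-test agrees. Analysis of covariance with age (17 df) stays at about 5% in every cell. With r = 0 the unadjusted rate is 5% at any gap.

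**Step 3, the rank test.** A separate simulation in years (ages kept within 18 to 60, slope 0.5 SD per 10 years) gave t-test rates of 6.8%, 12.2%, 20.3% and 31.8% at realised gaps of about 4, 8, 12 and 15 years. The Mann-Whitney rates were 6.0%, 10.6%, 18.0% and 28.2%. The nonparametric option is therefore little protection.

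**Step 4, masking.** With r = 0.35 and a 1 SD age gap working against a true difference of 1.32 SD, unadjusted power is about 54% and adjusted power about 73%.

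**Step 5, cost of adjusting.** 10 v 10 detects 1.32 SD with about 80% power unadjusted. If age is in fact unrelated to RLX, the adjusted test has about 77% power with no age gap, 74% at 0.5 SD, 67% at 1 SD and 57% at 1.5 SD, because group and age become collinear. With no age gap, adjustment gains power when age does matter: about 82% at r = 0.35 and 87% at r = 0.5.

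**Step 6, chance gaps.** If the age distributions were identical, the standardised gap would have SD √(2/10) = 0.447. A gap above 0.5 SD (0.5/0.447 = 1.118) would then arise in about 26% of comparisons. The 5% error rate still holds over repeated samples, as the first row of the table shows.

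**The case against.** The strongest reply is that neither condition is established. No age slope for RLX is given. The corpus luteum statement concerns RLX 2 in females and points to ovulatory status, not to age as such. Nothing links age to RLX 1, CSF levels or receptor affinity, which are also outcomes. No expected age is given for any group. All of this stands, and it is why the point is conditional. A reader might infer that the planned contrasts are biased by age; the documents do not support that.

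A reader might also infer that small samples make the problem likely, because sizeable chance gaps are common with 10 per group. That does not follow. Chance gaps are already part of the t-test's sampling variance, so they affect precision and the reading of one realised sample, not the error rate. Bias needs a systematic age difference between the groups. At 0.5 SD, moreover, the distortion is small.

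Adjustment also has a price. The power loss is largest exactly where the age gap is largest, and a linear model needs quantifiable values. The Assays section gives working ranges that start at 7.8 pg/mL for RLX 2 and 100 pg/mL for RLX 1, and does not say how many samples will fall below them. Both points are accepted and shape the fix.

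Finally, this is a 30-subject baseline study with no confirmatory decision attached, and age could be described by group under the present wording. That limits the severity, but nothing in the plan commits to doing so.

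**Conclusion.** The point holds in conditional form. The plan compares non-randomised, unmatched groups over a wide age range with tests that cannot take age into account. If RLX varies with age and the groups differ in age, the contrasts will mix the two. On the assumed values, false positives range from barely above 5% to about 36%, depending on the correlation and the gap. They stay at 5% if age is unrelated to RLX or the groups share the same expected age. The documents do not say where in this range the study lies.

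That age is known for every subject is inferred from the eligibility rule; no section lists it as an analysis variable. This is an inexpensive improvement to an exploratory study, not an error that invalidates it.

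**What to change.** Add to the Analysis section, in substance:

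- Age is summarised by group.
- The planned unadjusted test is kept.
- For each between-group comparison of RLX level and of receptor affinity, an age-adjusted difference with a 95% CI is also reported, from a linear model with group and age in years, on the log scale where the data are skewed.
- Where many values lie below the assay's working range, a rank-based or censored model with age replaces the linear one.
- The adjusted and unadjusted results are read side by side.

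This takes a few lines and no new data item, since age is needed for eligibility. The cost is the power loss in Step 5: about 3 points with no age gap, and much more with a wide one. A linear term may miss a step at menopause, and adjustment is unreliable if the groups' ages barely overlap. In that case the report should say that age and group cannot be separated. Matching on age at enrolment would protect power better, but it changes recruitment and goes beyond what this point requires.

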It is well-known that MS clinical disease activity abates during pregnancy, although the mechanism(s) of these changes are not understood. Investigations of estrogens and progesterone have not provided consistent data supporting their potential role in MS protection during pregnancy. Relaxin (RLX), a peptide member of the insulin superfamily, is dramatically up-regulated and plays an important role in pregnancy. It also is an immune regulator and may contribute to the autotolerance that seems to develop during pregnancy in females with MS. The data that supports a potential role for RLX as an auto-immune mediator, and a potential therapeutic agent in multiple sclerosis, is presented in the paragraphs that follow.

Perioxisomal Proliferator-activated Receptor-Gamma (PPARG):

PPARG is part of a superfamily of nuclear hormone, ligand-activated transcription factors, that are receptors with DNA-linked and C-terminal ligand-linked domains ¹¹. Ligand activation of these receptors results in reduced pro-inflammatory and increased anti-inflammatory gene expression. PPARG is also constitutionally expressed on T-cell lymphocytes and macrophages in the periphery¹², on

astrocytes and microglia within the CNS, and may not only regulate systemic immune responses, but also regulate inflammatory responses within the CNS¹³. PPARG agonists reduce T-cell proliferation ¹⁴, inhibit production of the proinflammatory cytokines IL-1B, IL-2, IL-6, IL-12 ¹⁵, interferon gamma (IFNG) and TNFa ¹⁴, and promote T-cell apoptosis ^{14, 16}. PPARG ligand agonists also inhibit expression of IFNG-stimulated pro-inflammatory chemokine production by endothelial cells¹⁷, thus potentially inhibiting inflammatory cell trafficking.

Thiazolidinedone (TZD) anti-glycemic agents, such as pioglitazone and rosiglitazone, are PPARG agonist ligands that have both antiglycemic and antiinflammatory properties ¹⁶. Pioglitazone and rosiglitazone inhibit mitogenstimulated T-cell proliferation, as well as TNFa and IFNG production¹⁴.

In experimental allergic encephalomyelitis (EAE), used as an animal model of MS, TZDs reduce lymphocyte proliferation and infiltration into the CNS¹⁸, block IL-12-induced TH0 differentiation into pro-inflammatory TH1 T cells¹⁹, reduce gene expression for IL-1B and IL-6, reduce production of TNFa and IFNG, and reduce clinical disease expression ¹⁴.

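### Does the 100 pg/mL floor of the RLX 1 assay, 12.8 times the RLX 2 floor, call for a range check or an out-of-range rule?

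*Combined protocol and SAP*

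**What the plan says.** The background section headed Relaxin biology overview describes "RLX 2 being the most abundant circulating form in humans". ASSAYS then gives the working range of each kit, both used in serum and CSF. For RLX 1: "The range of sensitivity of the assay is from 100-10000 pg/mL., and is linear within this range". For RLX 2: "The range of sensitivity of the assay has been demonstrated to be 7.8 to 500 pg/mL".

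No expected concentration is set against either range. RESEARCH STRATEGY explains why: "there is no information available on such fundamental guestions as what serum and CSF levels of RLX are observed in patients". The study exists to fill that gap. The background says relaxin "is dramatically up-regulated and plays an important role in pregnancy", but Subjects restricts enrolment: "All subjects will be age 18 to 60, non-pregnant females".

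The Analysis section is two sentences long. It promises descriptive statistics for each variable and, for group comparisons, "T-tests or nonparametric tests, depending on the type and distribution of the data". No section mentions a preliminary range check, dilution of samples above 500 pg/mL, or a rule for values outside the limits. There are three groups of 10, with no stated power, significance level or target effect.

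**The concern.** The two ranges look mismatched. If RLX 2 is the more abundant isoform, RLX 1 should need the more sensitive kit, yet its floor is far higher. The subjects are not pregnant, so the state in which relaxin rises sharply does not apply. Serum RLX 1 could therefore be largely unmeasurable.

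Three things would be at stake. A baseline level for RLX 1, one of the study's aims, could not be estimated well from mostly undetectable values. A comparison of RLX 1 between groups would lose power. Non-detects could also carry group information: the one abstract cited in the background reports that "patients diagnosed with MS had higher circulating levels of RLX" than controls, so undetectable values might gather in Group 3. A t-test or a mean cannot be computed on such values without a substitution or censoring rule, and none is stated. Group 2 has a lumbar puncture purely for research, so an analyte lost to an unchecked floor would be regrettable.

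**Working it through.** **Inputs from the documents.** RLX 1 range 100 to 10000 pg/mL and RLX 2 range 7.8 to 500 pg/mL (ASSAYS); RLX 2 the more abundant in circulation (Relaxin biology overview); 10 subjects in each of three groups (Subjects). The plan has no derived figure to reproduce.

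**Step 1: the limits.** Floor ratio: 100/7.8 = 12.8. If RLX 1 ≤ RLX 2 in an undiluted serum sample, both are in range only when 100 ≤ RLX 1 ≤ RLX 2 ≤ 500, a window of 500/100 = 5-fold. Both statements are correct. Diluting RLX 2 samples would raise the upper edge but not the lower one.

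**Step 2: does the window matter?** The Analysis section treats each variable separately and compares groups. It plans no ratio, pairing or joint model of the two isoforms. A sample with RLX 2 in range and RLX 1 out of range still contributes fully to the RLX 2 analysis. Only the RLX 1 floor remains relevant.

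**Step 3: how much data is exposed?** Planned concentrations: 30 subjects × 2 fluids × 2 isoforms = 120. The abundance statement concerns circulating relaxin and says nothing about CSF, so the argument covers serum RLX 1: 30 of 120.

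**Step 4: what would the floor cost?** This needs assumptions that the documents do not supply. Take log-normal levels with log-SD 1, RLX 2 centred at m, and a constant ratio r = RLX 2/RLX 1. The RLX 1 share below the floor at the centre is Φ(ln(100r/m)). With two groups at ±0.66 SD around the centre (d = 1.32, which gives an uncensored t-test 80% power at n = 10 per group), the group shares are Φ(ln(100r/m) ± 0.66). For m = √(7.8 × 500) = 62 and r = 1, these are Φ(0.471 + 0.66) = 87% and Φ(0.471 − 0.66) = 42%, averaging 65%. Power is for a tie-corrected Wilcoxon test with values below 100 tied (20,000 replicates). With nothing out of range it is 78%.

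| RLX 2 centre (pg/mL) | r | Below floor at centre | Below floor, mean of two groups | Power |
|---|---|---|---|---|
| 62 | 1 | 68% | 65% | 62% |
| 62 | 2 | 88% | 83% | 29% |
| 62 | 5 | 98% | 96% | 0.5% |
| 224 | 1 | 21% | 26% | 76% |
| 224 | 2 | 45% | 46% | 72% |
| 224 | 5 | 79% | 74% | 49% |

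A repeat run agreed to within about one percentage point. Type I error was at most 5.2%. The spread matters too: with RLX 2 at 62 and log-SD 0.5 or 1.5, power is 42% or 66% at r = 1, 0.1% or 51% at r = 2, and 0% or 16% at r = 5.

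**Step 5: reading the table.** With about 65% of values below the floor, power is 62/78 = 79% of its uncensored value. Further runs at log-SD 1 gave 70% power with 50% below, 54% with 71% below, 46% with 76% below and 30% with 83% below. Half of 78% is 39%, so half the power is gone only near 80% below the floor. A majority of values below 100 pg/mL does not by itself ruin the comparison.

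**Step 6: which assay?** RESEARCH STRATEGY refers to SIMOA assays and gives no limits, while ASSAYS names two ELISA kits by catalogue number. Every figure above applies only if the ELISAs are used.

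**The case for a change.** The strongest case for acting is that the mismatch is visible before any sample is run. Samples are frozen and sent as a batch, so a small group-blind check is feasible. An out-of-range rule costs one sentence, and fixing it beforehand removes a choice that would otherwise be made after group membership is known. If RLX 1 is several-fold lower than RLX 2, and RLX 2 itself is modest, the table shows power close to nil. Well before that point, a median reported only as below 100 pg/mL tells little about baseline levels.

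Part of this stands. No rule is written, a written one would be tidier, and heavy non-detection would leave a poor estimate of the RLX 1 level. But the severe rows need a ratio and a centre that the documents do not give, and other equally admissible inputs show almost no loss (76% or 72% against 78%). Stating expected levels in advance asks for what RESEARCH STRATEGY says is unknown. A pilot run uses part of the 5 mL of each fluid, with the volume per assay not given, and a replacement assay changes sourcing and cost. The clustering of non-detects in Group 3 rests on one abstract that names no isoform. If it happened, a rank test would use that information.

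**Conclusion.** No change is needed. The arithmetic on the limits is right: a 12.8-fold difference in floors, and a 100 to 500 pg/mL joint window if RLX 2 is at least as high as RLX 1. The joint window bears on no planned analysis, and what remains is an unquantified risk to 30 of 120 concentrations.

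The missing handling rule is a gap that analysts fill sensibly. A variable with many values at a limit is one whose distribution points to the nonparametric option the Analysis section already provides. Keeping such values, tying them at the limit and reporting the percentage detectable is ordinary practice, as is rerunning a diluted sample that reads above the top standard. In a descriptive study of 10 per group with no stated power target, a finding that serum RLX 1 is mostly undetectable would itself be baseline information.

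The power figures assume log-normal levels, a constant isoform ratio and a 1.32 SD difference. They show what could happen, not what will. Real levels mostly far below 100 pg/mL would make the loss for RLX 1 large, but nothing in the documents shows this to be likely. The SIMOA and ELISA wording differs between sections; that is a separate drafting matter, and it makes the limits used here less certain rather than strengthening the concern.
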